
• Primary objective:
– to evaluate the long-term safety and tolerability of vortioxetine in child and adolescent patients with a DSM-5™/diagnosis of MDD• Secondary objectives:
– to evaluate the long-term effectiveness of flexible doses of vortioxetine in a range of 5 mg/day to 20 mg/day on:
• depressive symptoms• clinical global impression• cognitive function• functionality		
Study Methodology		

• Interventional, multi-national, multi-site, open-label, flexible-dose, long-term extension study in child and adolescent patients with MDD who completed one of the double-blind, placebo-controlled, active-reference studies 12709A and 12710A.• The Baseline Visit of this extension study hereafter referred to as Baseline Extension A, will be Visit 12 (Completion Visit) of lead-in Study 12709A or 12710A.• The dosage of vortioxetine will be initiated at 5 mg/day for the first 2 days prior to receiving 10 mg/day.• The target dose is 10 mg/day; however the investigator has the possibility to adjust the dose in case of unsatisfactory response up to 20 mg or in case of dose-limiting adverse events. The dose can be up or down titrated with 5 mg/day. The patient should receive the same dose for 2 days before being up-titrated to a new dose. Changes in dosing may occur at any site visit during the treatment course at the investigator's discretion but the maximum dose may not exceed 20 mg/day.• The treatment period is 26 weeks. The total study duration per patient from Baseline Extension A to the end of follow-up will be approximately 30 weeks.• If possible, patients who withdraw are to be seen for a withdrawal visit as soon as possible and they will be contacted for a safety follow-up visit 4 weeks after withdrawal.• The study design is presented in Panel 1 and the scheduled assessments are summarised in Panel 2.• Investigators will not be informed about which treatment their patients received during the 12709A or 12710A study at the time of enrolling them into this open-label extension study.• For ethical and equity reasons patients who turned 18 years during the lead-in study 12710A can be enrolled into this extension study.		

Target Patient Population

- The patient is a male or female, child aged ≥ 7 and < 12 years or adolescent aged ≥ 12 and ≤ 18 years at Baseline Extension A.
- The patient must have completed Study 12709A or 12710A (Visit 12, Completion Visit) immediately prior to enrolment into this extension study.
- The patient had a primary diagnosis of a Major Depressive Disorder (MDD) at entry in study 12709A or 12710A, diagnosed according to DSM-5™.
- The patient is indicated for long-term treatment with vortioxetine according to the clinical opinion of the investigator.

Investigational Medicinal Products, Doses and Mode of Administration

- Vortioxetine – 5 mg/day, tablets, orally
- Vortioxetine – 10 mg/day, tablets, orally
- Vortioxetine – 15 mg/day, tablets, orally
- Vortioxetine – 20 mg/day, tablets, orally

The treatment should be given once a day, preferably in the morning.

Efficacy Assessments

- Assessment of depressive symptoms:
 - Investigator rated
 - Children Depression Rating Scale Revised version (CDRS-R)
- Assessment of Global Impression:
 - Investigator rated
 - Clinical Global Impression Scale – Severity of Illness (CGI-S)
 - Clinical Global Impression Scale – Global Improvement (CGI-I)
- Assessment of cognitive function:
 - Parent rated (children aged 7-11 years at Baseline Extension A)
 - Behaviour Rating Inventory of Executive Function (BRIEF) – Global Executive Composite (overall summary score) – Subscales (initiate, working memory, plan/organize, organization of materials, monitor, inhibit, shift and emotional control)
 - BRIEF – Metacognition Index – Subscales (initiate, working memory, plan/organize, self-monitor, organization of materials)
 - Patient rated (adolescents aged 12-18 years at Baseline Extension A)
 - Behaviour Rating Inventory of Executive Function – Adolescent version- (BRIEF-SR) – Global Executive Composite (overall summary score) – Subscales (working memory, plan/organize, organization of materials, task completion, monitor, inhibit, shift and emotional control)
 - BRIEF-SR – Metacognition Index – Subscales (working memory, plan/organize, organization of materials and task completion)
- Assessment of functionality:
 - Investigator rated
 - Children's Global Assessment Scale (CGAS)
 - Patient rated
 - The PedsQL Present Functioning Visual Analogue Scales (PedsQL VAS)

Safety Assessments

- Adverse Events (AEs)
- Paediatric Adverse Event Rating Scale (PAERS)
- Clinical safety laboratory tests, including reproductive hormones
- Vital signs
- Menstrual cycle (age of menarche, the length of the menstrual cycle)
- Weight/Height
- Electrocardiograms (ECGs)
- Physical examinations including Tanner scoring
- Columbia Suicide Severity Rating Scale (C-SSRS)

Endpoints

- Primary endpoint:
 - description of safety parameters, see safety endpoints below.
- Secondary endpoints:
 - depressive symptoms:
 - change from Baseline Extension A to Week 26 in CDRS-R total score
 - time to first relapse (CDRS-R value of ≥ 40)
 - time to first loss of remission (CDRS-R > 28)
 - Global Clinical Impression:
 - change from Baseline Extension A to Week 26 in CGI-S score
 - CGI-I score at Week 26. The assessment of the CGI-I should be in reference to Baseline A in the lead-in studies
 - cognitive function:
 - Children (7-11 years)
 - change from Baseline Extension A to Week 26 in BRIEF using the Global Executive Composite score
 - change from Baseline Extension A to Week 26 in BRIEF using the Metacognition Index
 - Adolescents (12-18 years)
 - change from Baseline Extension A to Week 26 in BRIEF-SR using the Global Executive Composite score
 - change from Baseline Extension A to Week 26 in BRIEF-SR using the Metacognition Index
 - functionality:
 - change from Baseline Extension A to Week 26 in CGAS score
 - change from Baseline Extension A to Week 26 in PedsQL VAS score
- Safety endpoints:
 - adverse events (AEs)
 - tolerability including assessment based on PAERS
 - Tanner score
 - absolute values and changes from Baseline Extension A in clinical safety laboratory tests, vital signs, weight, height, and ECG parameters
 - length of menstrual cycle
 - potentially clinically significant clinical safety laboratory test values, vital signs, weight, and ECG parameter values relative to Baseline Extension A
 - C-SSRS categorisation based on C-CASA definitions (1, 2, 3, 4, and 7)

Statistical Methodology

- The following analysis sets will be used to analyse and present the data:
 - *all-patients-treated set* (APTS) – all patients who took at least one dose of vortioxetine in the extension study.
 - *full-analysis set* (FAS) – all patients in the APTS with at least one valid post-Baseline Extension A assessment of the CDRS-R total score.
- The safety analyses will be based on the APTS.
- Descriptive statistics for all patients and by lead-in study and by treatment (n, arithmetic mean, standard deviation, median, minimum and maximum values) will be presented for continuous variables (values at each visit and, if relevant, changes from Baseline Extension A) and counts. If relevant, percentages will be presented for categorical variables.
- Analyses of safety endpoints:
 - Adverse events, PAERS items, Tanner scores, clinical safety laboratory tests, vital signs, height, weight, BMI, and ECG parameters will be summarised, and observed potentially clinically significant (PCS) safety laboratory test values will be flagged and summarised. The length of menstrual cycle and C-SSRS scores will be summarised using descriptive statistics.
 - The change from baseline will be derived with respect both to baseline in the lead-in studies and baseline in extension Study 12712A.
- The primary objective will be addressed with an overall clinical evaluation of the safety results.
- Adverse events occurring in the first two weeks of the study will be reported separately.
- The efficacy analyses will be based on the FAS.
- Analyses of efficacy endpoints:
 - Change from Baseline Extension A in CDRS-R, CGI-S, BRIEF, CGAS, and PedsQL VAS using descriptive statistics by lead-in study and by lead-in treatment.
 - CGI-I score at week 26 using descriptive statistics by lead-in study and by lead-in treatment.
 - Time to first relapse (CDRS-R value of ≥ 40) using Kaplan-Meier estimates.
 - Time to first loss of remission (CDRS-R > 28) using Kaplan-Meier estimates.
- For exploratory use a random effects slope and intercept model on safety and efficacy parameters will be applied using Mixed Model Repeated Measurements (MMRM) to study long-term development in safety and efficacy parameters (e.g. weight and CDRS-R).
- Summaries and analyses will be performed with respect to the Baseline in the lead-in studies.
- No interim analyses for efficacy are planned. A DMC will monitor safety data at regular intervals to be specified in the Data Monitoring Committee Charter.

Pharmacokinetic Analysis

Sparse PK samples (2) will be collected to measure vortioxetine plasma concentration. The population PK of vortioxetine will be assessed by means of nonlinear mixed effect modelling and the results from the analysis will be reported in a separate population PK report.

Sample Size Considerations

No formal sample size calculation has been performed for the present study, which includes patients who have completed the studies 12709A or 12710A and are eligible for enrolment for this study. Sample size is based on an expected withdrawal of 15-20% of the 1200 patients randomised to the lead-in studies. A maximum of 85% of these lead-in completers are expected to accept to continue into this extension study. This gives approximately 850 patients.

Ethical Rationale for Study and Study Design

In May 2014, WHO's "Health for the world's adolescents" report reveals that "depression is the predominant cause of illness and disability for both boys and girls aged 10 to 19 years" and adds that the "top 3 causes of adolescent deaths globally are road traffic injuries, HIV/AIDS, and suicide. Worldwide, an estimated 1.3 million adolescents died in 2012". The prevalence of Major Depressive Disorder (MDD) is estimated to be approximately 2% in children and 4% to 8% in adolescents.

Only one antidepressant, fluoxetine, is currently approved in Europe for the treatment of MDD in children and adolescents. In the US only fluoxetine is approved for use in children and fluoxetine and escitalopram for use in the adolescent population. Development of a new antidepressant will increase and strengthen the pharmacological treatment options for this patient population. This study is an extension study to Studies 12709A and 12710A and part of the agreed EMA Paediatric Investigational Plan (PIP) and the US Pediatric Written Request (PWR) for vortioxetine with the purpose to investigate the long-term safety and tolerability of vortioxetine in paediatric patients aged 7-17 years. It is the expectation that this study will demonstrate a favourable safety and tolerability profile, and therefore a positive benefit-risk ratio for the use of vortioxetine in the paediatric population.

Vortioxetine is approved in the US, EU and a number of other countries for the treatment of MDE/MDD in the adult population. The evaluation of the safety and tolerability of vortioxetine is based on data from a large clinical development programme in adult and elderly patients. In the overall clinical development programme treatment with vortioxetine at the therapeutic doses (5-20 mg/day) was safe and well tolerated. The approved recommended dose range of 5-20 mg/day for adults was evaluated in a pharmacokinetic and tolerability study performed in the paediatric population (aged 7 to 17 years) designed to guide the choice of doses to be used in the planned paediatric programme. Hence the chosen doses of vortioxetine (5, 10, 15 and 20 mg/day) for this study is based on the results from the paediatric pharmacokinetic and tolerability study and the knowledge from the adult studies.

As extrapolation of adult safety data is not considered appropriate for the paediatric population; a specific paediatric study is warranted to thoroughly address the long-term safety/tolerability of vortioxetine in the paediatric population. The 26-week treatment period is in alignment with treatment guidelines in EU and US that recommend continuation therapy with an antidepressant for at least 6 months in children and adolescents. Patients will be asked to attend the investigational clinic at regular intervals to ensure an adequate follow-up. The visits will be performed either as a visit in an outpatient clinic or as a phone call. In order to minimize potential pain, distress, and fear, patients will be seen in facilities which will be appropriate for childcare; the study personnel who interact with the patients will be experienced health care professionals (physicians with paediatric qualification, qualified paediatric nurses or psychologists); their education, training and experience will be documented. Age-appropriate explanations will be given to the child/adolescent prior to any investigation or procedure, in order to decrease anxiety and anticipation of pain. Potentially painful procedures such as venepuncture will be minimised with the use of topical anaesthesia before venepuncture. Blood sampling will be limited to the minimum required for obtaining valid data for evaluation. The number of blood samples and visits has been carefully evaluated against the value for the overall objectives of the study.

[figure not shown]
The investigator plays an important role in protecting the safety of the patient. The assessment of potential burden and risk is defined specifically in the clinical study protocol (safety rating scales, recording of adverse events, clinical safety laboratory tests (blood biochemistry, haematology and urine analysis), vital signs (blood pressure and pulse rate), weight, height, electrocardiogram and physical examination) and these will be evaluated by the investigator at each visit to ensure the patients' safety and well-being. If it does not remain in the patient's best interest to stay in the study, the investigator will ensure that the patient is withdrawn. Patients that are withdrawn from the study and do not complete, will be treated according to normal clinical practice.

In accordance with Good Clinical Practice, qualified medical personnel at Lundbeck will be available to advice on study-related medical questions. Medical monitoring and safety surveillance will be performed throughout the study according to Lundbeck standard procedures, and Lundbeck will regularly monitor and re-examine the balance of risks and benefit of the full clinical study, so that the health and well-being of paediatric patients enrolled will be safeguarded.

The selection criteria exclude the participation of patients at significant risk of suicide, and patients becoming at significant suicidal risk during the study will be withdrawn. Throughout the study, potential suicidal risk will be assessed both by rating scale (Columbia-Suicide Severity Rating Scale) and by the investigator's judgment.

An independent Data Monitoring Committee will be established in order to review the safety and tolerability data throughout this study. The same DMC will cover all the clinical studies in the paediatric vortioxetine program.

Panel 1 Study Design

Panel 2 Study Procedures and Assessments

Visit	Base-line Extension A	Treatment Period												Completion /Withdrawal ^a	Safety Follow-up ^b
		1	2	3	4 ^c	5	6 ^c	7	8 ^c	9	10 ^c	11	12 ^c		
Visit Number	1	2	3	4 ^c	5	6 ^c	7	8 ^c	9	10 ^c	11	12 ^c	13	14	
End of Week	0	1	2	3	4	6	8	10	12	15	18	22	26	30	
Visit Window ^d (days relative to nominal visit)	0	± 2	± 2	± 2	± 2	± 2	± 2	± 2	± 2	± 2	± 5	± 5	± 5	± 5	
Baseline Extension A Procedures and Assessments															
Signed informed consent/assent	✓														
Inclusion/exclusion criteria	✓														
Efficacy Assessments															
CDRS-R	✓ ^e	✓	✓			✓		✓		✓		✓		✓	
CGI-S	✓ ^e	✓	✓			✓		✓		✓		✓		✓	
CGI-I ^f	✓ ^e	✓	✓			✓		✓		✓		✓		✓	
BRIEF (7-11 years at Baseline Extension A)	✓					✓		✓		✓		✓		✓	
BRIEF-SR (12-18 years at Baseline Extension A)	✓					✓		✓		✓		✓		✓	
CGAS	✓ ^e					✓		✓		✓		✓		✓	
PedsQL VAS (PRO)	✓ ^e					✓		✓		✓		✓		✓	
Vortioxetine Quantification															
Blood sampling vortioxetine quantification	✓ ^e					✓								✓	
Safety Assessments															
Adverse events	✓ ^g	✓	✓	✓	✓	✓	✓	✓	✓	✓	✓	✓	✓	✓	✓ ^h
Blood and urine sampling for clinical safety laboratory tests	✓ ^{e,i}					✓								✓	
Vital signs	✓ ^e	✓	✓			✓		✓		✓		✓		✓	
Weight and height	✓ ^e									✓				✓	
Menstrual cycle and Tanner score	✓									✓				✓	
ECGs	✓ ^e					✓								✓	
Examinations (physical and neurological)	✓ ^e									✓				✓	
PAERS	✓ ^e	✓	✓	✓	✓	✓	✓	✓	✓	✓	✓	✓	✓	✓	
C-SSRS	✓ ^e	✓	✓	✓	✓	✓	✓	✓	✓	✓	✓	✓	✓	✓	

Visit	Base-line Extension A	Treatment Period												Completion /Withdrawal ^a	Safety Follow-up ^b
Visit Number	1	2	3	4 ^c	5	6 ^c	7	8 ^c	9	10 ^c	11	12 ^c	13	14	
End of Week	0	1	2	3	4	6	8	10	12	15	18	22	26	30	
Visit Window ^d (days relative to nominal visit)	0	±2	±2	±2	±2	±2	±2	±2	±2	±2	±5	±5	±5	±5	
Other Study Procedures															
IMP dispensed	✓	✓	✓		✓		✓		✓		✓				
Possible change in IMP dose		✓	✓		✓		✓		✓		✓				
IMP returned and IMP accountability		✓	✓		✓		✓		✓		✓		✓		
Recent and concomitant medication	✓ ^g	✓	✓	✓	✓	✓	✓	✓	✓	✓	✓	✓	✓		
Pregnancy test ^j	✓ ^e				✓								✓		
Drug and alcohol screen ^{e,k}															

- a This visit should take place as soon as possible after the patient withdraws from the study.
- b This can be a telephone contact, unless an SAE has occurred since the last visit or unless there was a clinically significant abnormal safety laboratory test value at the last visit. In such cases, safety follow-up(s) must be scheduled to allow for a medical examination and/or blood/urine sampling. Further safety follow-up visits beyond 30 days may be needed as judged by the investigator (if further safety follow-up visits are performed, these must be recorded in the patient's medical record, and not in the eCRF).
- c A telephone contact. The patient and/or legal representative and/or the investigator can request an unscheduled site visit to discuss their current dose. During such an unscheduled site visit, the CDRS-R, CGI-S, CGI-I, PAERS and C-SSRS must be performed.

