## 1.2 Secondary Objectives

- Secondary objectives:
  - to evaluate the long-term effectiveness of flexible doses of vortioxetine in a range of 5 mg/day to 20 mg/day on:
    - depressive symptoms
    - clinical global impression
    - cognitive function
    - functionality
  - to evaluate the palatability and acceptability of vortioxetine oral drops

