## 12 Safety

### 12.1 Adverse Events

#### 12.1.1 General Methodology for Adverse Events

Unless otherwise specified, tables, graphs, and listings will be based on the APTS.

All the tables will be presented for all patients and by lead-in study and by lead-in treatment, respectively, unless otherwise specified.

Tables by preferred term and tables by system organ class (SOC) and preferred term will be sorted in descending order by the overall percentage of patients.

Unless otherwise specified, the summaries of adverse events will include the total number and percentage of patients with an adverse event, and the total number of events. For sex-specific preferred terms, the denominator in the % calculations will be the number of patients of that sex. Sex-specific preferred terms will be marked in the summaries.

In summaries of adverse events presented by intensity, the maximum intensity of the adverse event will be used for patients who have more than one intensity of that event. Adverse events for which information on intensity is missing will be classified as severe.

Listings of adverse events will be sorted by site, lead-in study, lead-in treatment, patient number, and adverse event start date, and include preferred term, investigator term, adverse

event start date, days since first dose of IMP, duration of the adverse event, date of death, action taken, causality, intensity, seriousness, and outcome. For adverse events that change in intensity, each intensity will be included.

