#### **12.1.2.3 Classification of Adverse Events**

Adverse events will be classified according to the time of onset of the adverse events:

- *Lead-in adverse event* – an adverse event starts before visit 1 in 12712A and ongoing from (= with start date in) lead-in study 12709A or 12710A
- *treatment-emergent adverse event* – an adverse event that starts or increases in intensity/or seriousness at or after visit 1 of study 12712A

An adverse event is considered causally related to the use of the IMP when the causality assessment by the investigator is *probable* or *possible*.

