#### **12.1.2.4 Assigning Adverse Event Records to an Analysis Phase**

All records for an adverse event will be assigned to an analysis phase. The analysis phase will determine how an adverse event record is reported, and an adverse event may be reported in more than one analysis phase insofar as it worsens.

For further details, see [Data Handling Plan](#).

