### **12.1.3 Summary of All Adverse Events**

All adverse events will be listed, including a flag for TEAE.

An overview of the PYE, numbers, and percentages of patients with TEAE, serious adverse events (SAEs), or adverse events leading to withdraw, and of patients who died will be

provided for APTS. For TEAE, SAEs, and adverse events leading to withdrawal, the total number of events will be included.

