#### **12.1.5 Summary of Treatment-emergent Adverse Events**

The following summaries will be provided for the APTS:

- TEAE by SOC and preferred term
- TEAE by preferred term
- TEAE with an incidence > 2% and 5% by preferred term
- Causally related TEAE by SOC and preferred term
- TEAE by intensity (*mild/moderate/severe*), and preferred term
- Causally related TEAE by intensity and preferred term

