## 17 Changes to Analyses Specified in the Protocol

The following changes have been made as compared to the latest version of the protocol:

- C-SSRS categorisation has been updated and will no longer include C-CASA.
- Treatment emergent adverse events (TEAE) in 12712A is defined as an adverse event that starts or increases in intensity or seriousness after visit 1 of study 12712A.
- The analyses regarding time to first relapse and time to first loss of remission have been removed
- The analysis of random slope and intercept has been removed

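### The protocol synopsis promises separate reporting of adverse events in the first two weeks, but no adverse-event output in the SAP provides it and SAP 17 does not record its removal

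*Protocol*

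**What the plan says.** The Protocol Synopsis, under Statistical Methodology, commits without condition: "Adverse events occurring in the first two weeks of the study will be reported separately". Protocol 17.10.1 does not repeat this. It makes allocation of treatment-emergent events (TEAEs) to study periods optional and leaves the definition of any periods to the SAP.

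SAP 12.1.5 opens its list with "The following summaries will be provided for the APTS" and names six summaries, none tied to time of onset. SAP 12.1.1 sets the standard layout: "All the tables will be presented for all patients and by lead-in study and by lead-in treatment, respectively, unless otherwise specified". SAP 12.1.3 adds: "All adverse events will be listed, including a flag for TEAE"; under SAP 12.1.1 the listings carry days since first dose. SAP 12.1.2.4 assigns each record to an analysis phase and says "The analysis phase will determine how an adverse event record is reported", with details left to the Data Handling Plan.

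SAP 17 introduces its list with "The following changes have been made as compared to the latest version of the protocol" and gives four items.

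**The concern.** Long-term safety and tolerability is the primary objective, and the protocol singles out one early window for its own report. Every patient restarts at 5 mg/day for two days and then goes to 10 mg/day, whatever the lead-in treatment was. Because the lead-in studies had placebo and active-reference arms, some patients meet vortioxetine for the first time here.

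A table that pools 26 weeks shows who had an event but not when. If the SAP is the working instruction, the programmed output will contain no early-event summary, and the study report will have no recorded reason for its absence.

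**Working it through.** This is a comparison of texts; the plan gives no figure to reproduce.

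**Step 1: look for the output in the SAP.**

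| SAP section | Output | Limited to first two weeks? |
|---|---|---|
| 12.1.3 | Overview table; listing of all events | No |
| 12.1.4 | Lead-in events by preferred term | No |
| 12.1.5 | Six TEAE summaries (class, term, incidence cut-offs, causality, intensity) | No |
| 12.1.6 | Listing for patients who died | No |
| 12.1.7, 12.1.8 | Serious events; events leading to withdrawal | No |
| 12.1.9 | Nausea incidence and prevalence per four weeks | No; one term, longer interval |
| 12.1.10 | Events of special interest | No |

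**Step 2: look for a period definition.** SAP 18.1 has the word Period in its heading but defines only the baseline. The SAP's one 14-day category is in section 9 and applies to exposure. Protocol 17.10.1 left any periods to the SAP, and the SAP text names none.

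**Step 3: look for a recorded removal.** The four items in SAP 17 are the end of C-CASA categorisation, the TEAE definition, removal of the two time-to-event analyses (relapse and loss of remission), and removal of the random slope and intercept model. None concerns early adverse events. The last two remove analyses that stand in the same synopsis list as the two-week sentence.

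Result: no adverse-event output is restricted to the window, and 0 of 4 recorded changes mention it.

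**Step 4: what a 26-week total can hide (illustration only).** The documents give no onset profile, so every input except the planned 850 patients and the 182 days is an assumption. Suppose there are no withdrawals, that 10% of patients (85) report a given term over 26 weeks, and that the onset rate in Days 1-14 is *k* times the rate in Days 15-182.

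- Cumulative hazard: H = -ln(1 - 0.10) = 0.105.
- Early share: s = 14k / (14k + 168).
- Patients with first onset in Days 1-14: 850 × (1 - exp(-H × s)).

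| k | s | Early patients, 10% term | Early patients, 5% term |
|---|---|---|---|
| 1 | 7.7% | 6.9 of 85 | 3.3 of 42.5 |
| 2 | 14.3% | 12.7 | 6.2 |
| 5 | 29.4% | 25.9 | 12.7 |
| 10 | 45.5% | 39.7 | 19.6 |

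The planned preferred-term table shows the same total in every row.

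Nausea is less affected. For a 10% term, the early share over the first four weeks is (14k + 14) / (14k + 168), which gives 13.7, 19.0, 31.0 and 43.6 patients. Days 1-14 supply 50%, 67%, 84% and 91% of these. The four-week interval is thus a partial substitute, for that one term.

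**The case against.** The strongest reply is that both halves of the point depend on documents that are not public.

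- **Protocol version.** SAP 17 compares itself with the latest protocol. The SAP has an objective "to evaluate the palatability and acceptability of vortioxetine oral drops", which the public protocol lacks and SAP 17 does not list as a change. SAP 18.4 says the CDRS-R was rated only at Weeks 0, 12 and 26 before the second amendment. The public protocol already has the denser schedule, so a still later version is plausible, and it may not contain the two-week sentence. This stands. The two removals that SAP 17 does list show that part of the same synopsis text was carried forward, but they do not prove that this sentence was.
- **Data Handling Plan.** It may define an early phase. This also stands as a possibility. However, assigning records to a phase is not an output, and no summary in SAP 12.1.5 is said to be by phase.
- **Weak commitment.** The sentence appears only in the synopsis, does not ask for a particular table, and sits beside optional wording in the body. That lowers its weight. But the optional wording concerns study periods in general and does not withdraw a specific, unconditional statement.
- **Recoverable data.** Every event is listed with days since first dose. True, but counting by hand from listings is not a pre-specified summary.

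A reader might also infer that the window was set to catch effects of starting or switching to vortioxetine. The protocol gives no reason for it, so that rationale is an inference.

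**Conclusion.** The mismatch holds: the public protocol states an early adverse-event output, and the public SAP neither provides it nor records dropping it. It is a minor but real omission on the primary objective. What is lost is one stated result and the record of why it is absent. The counts in the illustration show only that a total does not reveal timing; they are not an estimate for this drug.

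Two stronger readings are tempting. One is that the sponsor removed the report without saying so. The documents cannot show this, because the protocol version that SAP 17 refers to and the Data Handling Plan are both unseen. The other is that the safety results would be biased or early events lost. Neither follows: the summaries are descriptive, and the events are collected and listed.

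**What to change.** Do one of the following in the SAP.

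1. Add one summary to SAP 12.1.5: TEAEs with onset from Visit 1 through Day 14 (Day 1 being the first dose in 12712A), by preferred term, on the APTS, for all patients and by lead-in study and lead-in treatment. Starting at Visit 1 matches SAP 12.1.2.3, which defines a TEAE as "an adverse event that starts or increases in intensity/or seriousness at or after visit 1 of study 12712A".
2. If the Data Handling Plan already has an early phase, state in SAP 12.1.5 that TEAEs are summarised for it.
3. If the output was dropped on purpose, list that in SAP 17 with the reason.

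The first option is an existing table rerun with an onset-date filter on data already collected. Incomplete start dates would follow the imputation that SAP 18.5.4 refers to the Data Handling Plan, so that rule should be checked against the window. The downside is a few more table pages and small counts in some lead-in arms. Flags for serious events or withdrawals, and a companion table from Day 15, go beyond what the protocol promised and are not required.
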